7.8.5. Etoposide

Safety management guidelines for etoposide are in accordance with the prescribing information {ETOPOPHOS 2019}. Key considerations are described here.

Myelosuppression

Etoposide when given as an anti-leukemic regimen can cause severe myelosuppression. Close monitoring of laboratory counts, infectious prophylaxis, and supportive blood products and growth factors is needed. Etoposide should only be administered by physicians experienced with treating AML.

Hypersensitivity Reactions

Hypersensitivity reactions to etoposide, including anaphylaxis, can occur. If hypersensitivity reactions occur, immediately interrupt treatment with etoposide and institute supportive management per local guidelines. Permanently discontinue etoposide treatment in any patient who experiences a severe hypersensitivity reaction.

Secondary Leukemias

Secondary leukemias have been observed with etoposide. Further details are provided in the prescribing information {ETOPOPHOS 2019}.

7.8.6. Cytarabine

Safety management guidelines for cytarabine are in accordance with the prescribing information {CYTARABINE 2020}. Key considerations are described here.

Myelosuppression

Cytarabine can cause severe myelosuppression. Close monitoring of laboratory counts, infectious prophylaxis, and supportive blood products and growth factors is needed. Cytarabine should only be administered by physicians experienced with treating AML.

Neurotoxicity

Neurotoxicity has been observed with high-dose cytarabine use. Neurologic symptoms vary but range from somnolence and ataxia to more severe complications such as seizures and even death. Close monitoring for neurologic toxicities, including monitoring for signs and symptoms, neurologic examinations, and imaging (if pertinent) should be conducted. Supportive care measures per institutional guidelines should be instituted for observed neurotoxicities. For severe neurotoxicities, cytarabine should be discontinued.

Hypersensitivity Reactions

Hypersensitivity reactions to cytarabine, including anaphylaxis, can occur. If hypersensitivity reactions occur, immediately interrupt treatment with cytarabine and institute supportive management per local guidelines. Permanently discontinue cytarabine treatment in any patient who experiences a severe hypersensitivity reaction.

7.8.7. CC-486

Safety management guidelines for CC-486 are in accordance with the prescribing information {ONUREG 2020}. Key considerations are described here.

Myelosuppression

CC-486 can cause myelosuppression. Complete blood counts should be performed at least every other week for the first 2 cycles and at least prior to each cycle thereafter.

Hypersensitivity Reactions

CC-486 can cause hypersensitivity reactions. Treatment with CC-486 should be discontinued in any patient who experiences a severe hypersensitivity reaction.

Risk of Substitution with Other Azacitidine Products

CC-486 should not be substituted for IV or SC azacitidine. The indications and dosing of CC-486 differ from those of azacitidine.

8. STATISTICAL CONSIDERATIONS

8.1. Analysis Objectives and Endpoints

8.1.1. Analysis Objectives

Objectives are presented in Section 2.

8.1.2. Primary Endpoints

The primary endpoints for the Phase 2 cohorts are as follows:

- Rate of Complete Remission (Phase 2 Cohorts 1 and 2): The CR rate is defined as the proportion of patients who achieve CR (CR_{MRD} or complete remission with positive or unknown MRD [CR_{MRD}) as determined by the investigator based on prespecified criteria (Appendix 7) while on study prior to initiation of any new anti-AML therapy.
- Minimal Residual Disease Negative Complete Remission Rate (Phase 2 Cohort 3): The MRD negative CR rate is defined as the proportion of patients who maintain CR as determined by the investigator based on prespecified criteria (Appendix 7) and reach MRD negative disease status on 2 consecutive bone marrow assessments as determined using multiparameter flow cytometry with a sensitivity of < 0.1% while on study prior to initiation of any new anti-AML therapy. For this cohort, patients will need to have 2 consecutive MRD negative values to be considered MRD negative for analysis.

The primary endpoint for the safety run-in cohorts is as follows:

• Incidence of DLTs, as defined in Section 3.1.1.2, and incidence of treatment-emergent AEs and laboratory abnormalities according to the NCI CTCAE Version 5.0

8.1.3. Secondary Endpoints

The secondary efficacy endpoints are as follows:

- Overall Response Rate (Cohorts 1 and 2): The ORR is the proportion of patients who achieve CR (CR_{MRD}- or CR_{MRD+/unk}), CRi, CRh, PR, or MLFS as determined by the investigator based on prespecified criteria (Appendix 7) while on study prior to initiation of any new anti-AML therapy.
- Complete Remission Rate/Complete Remission with Incomplete Hematologic Recovery (Cohorts 1 and 2): The CR/CRi rate is the proportion of patients who achieve CR (CR_{MRD}- or CR_{MRD+/unk}) or CRi as determined by the investigator based on prespecified criteria (Appendix 7) while on study prior to initiation of any new anti-AML therapy.

- Minimal Residual Disease Negative Complete Remission Rate (Cohorts 1 and 2): The CR_{MRD} rate is the proportion of patients who achieve a CR_{MRD} as determined by the investigator based on prespecified criteria (Appendix 7) while on study prior to initiation of any new anti-AML therapy.
- Complete Remission or Complete Remission with Partial Hematologic Recovery Rate
 (Cohorts 1 and 2): The CR/CRh rate is the proportion of patients who achieve CR (CR_{MRD}
 or CR_{MRD+/unk}) or CRh as determined by the investigator based on prespecified criteria
 (Appendix 7) while on study prior to initiation of any new anti-AML therapy.
- Cytogenetic Complete Remission (Cohorts 1 and 2): The cCR rate is the proportion of patients who achieve cCR determined by investigator based on the prespecified criteria (Appendix 7) while on study prior to initiation of any new anti-AML therapy.
- Duration of Response (Cohorts 1 and 2): The DOR is measured from the time assessment criteria are met for CR (CR_{MRD}- or CR_{MRD+/unk}), CRi, CRh, PR, or MLFS, whichever is first recorded, until the first date of AML relapse, progressive disease, or death (including assessments post SCT). Those who are not observed to have a relapse, progressive disease, or death will be censored at the date of their last response assessment. If patients start taking new anti-AML therapies (except SCT and post SCT maintenance treatment) before relapse, duration of response will be censored at the last response assessment before the initiation of the new anti-AML therapies.
- Duration of Complete Remission (Cohorts 1 and 2): The duration of CR is measured from the time the assessment criteria are first met for CR (CR_{MRD} or CR_{MRD+/unk}) until the first date of AML relapse or death (including assessments post SCT). Those who are not observed to have relapsed disease or death will be censored at the date of their last response assessment. If patients start taking new anti-AML therapies (except SCT and post SCT maintenance treatment) before relapse, duration of CR will be censored at the last response assessment before the initiation of the new anti-AML therapies.
- Duration of Complete Remission or Complete Remission with Incomplete Hematologic Recovery (Cohorts 1 and 2): The duration of CR/CRi is measured from the time the assessment criteria are first met for CR (CR_{MRD}- or CR_{MRD+/unk}) or CRi until the first date of AML relapse or death (including assessments post SCT). Those who are not observed to have relapsed disease or death will be censored at the date of their last response assessment. If patients start taking new anti-AML therapies (except SCT and post SCT maintenance treatment) before relapse, duration of CR + CRi will be censored at the last response assessment before the initiation of the new anti-AML therapies.
- Duration of Complete Remission or Complete Remission with Partial Hematologic Recovery (Cohorts 1 and 2): The duration of CR/CRh is measured from the time the assessment criteria are first met for CR (CR_{MRD}- or CR_{MRD}+/_{unk}) or CRh until the first date of AML relapse or death (including assessments post SCT). Those who are not observed to have relapsed disease or death will be censored at the date of their last response assessment. If patients start taking new anti-AML therapies (except SCT and post SCT maintenance treatment) before relapse, duration of CR + CRh will be censored at the last response assessment before the initiation of the new anti-AML therapies.

CONFIDENTIAL Page 114 02 November 2023

- Event-Free Survival (Cohorts 1 and 2): EFS is defined as the time from the date of the first dose of study treatment to the earliest date of documented relapse from CR, treatment failure (defined as failure to achieve CR before the fifth cycle of magrolimab+venetoclax+azacitidine in Phase 2 Cohort 1 and before the third cycle of magrolimab + MEC in Phase 2 Cohort 2), or death from any cause. Response assessments post SCT will be included in the analysis. Deaths post SCT or new anti-AML therapies (except SCT and post SCT maintenance) will be included. Those who are not observed to have one of these events during the study will be censored at the date of their last response assessment during the study. Day 1 of treatment will be assigned as the event date for patients with treatment failure.
- Minimal Residual Disease Negative Complete Remission or Complete Remission with Incomplete Hematologic Recovery Rate (Cohort 3): The MRD negative CR/CRi rate is defined as the proportion of patients who maintain CR/CRi as determined by the investigator based on prespecified criteria (Appendix 7) and reach MRD negative disease status on 2 consecutive bone marrow assessments as determined using multiparameter flow cytometry with a sensitivity of < 0.1% while on study prior to initiation of any new anti-AML therapy.
- Relapse-Free Survival (Cohort 3): RFS is measured from the time of the first dose of study treatment until the first date of AML relapse or death from any cause, whichever comes first. Those who are not observed to have relapsed disease or death will be censored at the date of their last response assessment during the study.
- Duration of Minimal Residual Disease Negative Complete Remission (Cohort 3): The duration of MRD negative CR is measured from the time the patient achieves MRD negative status (first of the 2 consecutive MRD negative bone marrow assessments) and maintains CR until the first date of AML relapse, loss of MRD negative status, or death (including assessments post SCT). Those who are not observed to have relapsed disease, loss of MRD negative status, or death will be censored at the date of their last response assessment. If patients start taking new anti-AML therapies (except SCT and post SCT maintenance treatment) before relapse, duration of MRD negative CR will be censored at the last response assessment before the initiation of the new anti-AML therapies.
- Duration of Minimal Residual Disease Negative Complete Remission or Complete Remission with Incomplete Hematologic Recovery (Cohort 3): The duration of MRD negative CR/CRi is measured from the time the patient achieves MRD negative status (first of the 2 consecutive MRD negative bone marrow assessments) and maintains CR/CRi until the first date of AML relapse, loss of MRD negative status, or death (including assessments post SCT). Those who are not observed to have relapsed disease, loss of MRD negative status, or death will be censored at the date of their last response assessment. If patients start taking new anti-AML therapies (except SCT and post SCT maintenance treatment) before relapse, duration of MRD negative CR + CRi will be censored at the last response assessment before the initiation of the new anti-AML therapies.

- Overall Survival: The OS is measured from the date of the first dose of study treatment to the
 date of death from any cause. Those who are not observed to die during the study will be
 censored at last date they are known to be alive.
- Red Blood Cell Transfusion Independence Rate: The RBC transfusion independence rate is
 the proportion of patients who have a 56-day or longer period with no RBC or whole blood
 transfusion at any time between the date of the first dose and discontinuation of study
 treatment among all patients who are RBC transfusion-dependent at baseline, defined as
 having received an RBC or whole blood transfusion within the 28 days prior to the first dose
 of study treatment (conversion rate), and among all patients who are RBC
 transfusion-independent at baseline (maintenance rate).
- Platelet Transfusion Independence Rate: The platelet transfusion independence rate is the
 proportion of patients who have a 56-day or longer period with no platelet transfusions at any
 time between the date of the first dose and discontinuation of study treatment among all
 patients who are platelet transfusion-dependent at baseline, defined as having received a
 platelet transfusion within the 28 days prior to the first dose of study treatment (conversion
 rate), and among all patients who are platelet transfusion independent at baseline
 (maintenance rate).

The secondary safety endpoint is as follows (Phase 2 cohorts):

 Incidence of treatment-emergent AEs and laboratory abnormalities according to the NCI CTCAE Version 5.0

The secondary PK endpoint is as follows:

 PK concentrations of magnolimab in combination with venetoclax and azacitidine; mitoxantrone, etoposide, and cytarabine; or CC-486

The secondary immunogenicity endpoint is as follows:

Rate and magnitude of anti-magnolimab antibody incidence and prevalence

CONFIDENTIAL Page 116 02 November 2023

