8.3. Analysis Conventions

8.3.1. Analysis Sets

8.3.1.1. Efficacy

The primary analysis set for efficacy analysis is the Full Analysis Set (FAS). The FAS includes all enrolled patients who receive at least 1 dose of any study treatment, with treatment group designated according to the assigned treatment.

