8.5.2. Secondary Analyses

The point estimates of the ORR, CR rate, CR/CRi rate, CR_{MRD} rate, cCR rate, and CR/CRh rate and the corresponding 2-sided exact 95% CIs based on the Clopper-Pearson method will be provided for Cohorts 1 and 2. The analyses of RBC and platelet transfusion independence rates (conversion rate and maintenance rate) will be similar to those of ORR.

Medians, first quartile (Q1), and third quartile (Q3) of EFS distribution, and the proportion of patients who are event free at Weeks 12, 24, and 48 from the first dosing date will be estimated by cohort using the KM method and the corresponding 95% CIs will be reported. Kaplan-Meier plots will be provided. Analyses of OS will be similar to those of EFS.

For the time-to-event endpoints of duration of CR, duration of CR/CRi, duration of CR/CRh, DOR, RFS, duration of MRD negative CR, and MRD negative CR/CRi, analyses will be conducted on the subsets for which the outcome measures are defined. Specifically, the duration of CR, duration of CR/CRi, duration of CR/CRh, and DOR will be based on patients in Cohorts 1 and 2 who achieve CR, CR/CRi, CR/CRh, and OR, respectively. The RFS will be analyzed for Cohort 3, duration of MRD negative CR will be based on patients in Cohort 3 who achieve MRD negative status and maintain CR, and the duration of MRD negative CR/CRi will be based on patients in Cohort 3 who achieve MRD negative status and maintain CR/CRi. The KM method will be used to estimate median durations and 95% CIs, and KM plots will be provided.

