Appendix Table 11. Additional Response Definitions Used in This Study (2003 IWG Criteria)

	Definitions						
Response Criteria	Neutrophils	Platelets	Bone Marrow Blasts	Other			
Cytogenetic CR (cCR)	> 1.0 × 10 ⁹ /L	> 100 × 10 ⁹ /L	< 5%	Cytogenetics normal and no evidence of extramedullary disease			

cCR = cytogenetic complete remission; CR = complete remission; IWG = International Working Group Source: {Cheson 2003}

Treatment Failure

Treatment failure is defined as failure to achieve complete remission (CR) before the fifth cycle of magrolimab+venetoclax+azacitidine in Cohort 1 and before the third cycle of magrolimab + MEC in Cohort 2.

a Not in the ELN 2017 guidelines. Modification for the purpose of this protocol. A response could be classified as both CRh and CRi if both criteria are met.

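### Section 8.1.3 limits the EFS treatment-failure event to Phase 2 patients, but Appendix 7 applies it to the whole cohort, so run-in patients without CR get conflicting outcomes and the 8.1.3 wording biases EFS upward

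*Protocol*

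**What the plan says.** Protocol Section 8.1.3 introduces the endpoint for both cohorts without restriction: "Event-Free Survival (Cohorts 1 and 2): EFS is defined as the time from the date of the first dose of study treatment". The events are relapse from CR, treatment failure, and finally "or death from any cause. Response assessments post SCT will be included in the analysis". Treatment failure means no CR ahead of the fifth cycle of "magrolimab+venetoclax+azacitidine in Phase 2 Cohort 1 and before the third cycle of magrolimab + MEC in Phase 2 Cohort 2". Two further rules in the same bullet matter here: "Day 1 of treatment will be assigned as the event date for patients with treatment failure", and "Those who are not observed to have one of these events during the study will be censored at the date of their last response assessment".

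Appendix 7, in the treatment-failure paragraph below Appendix Table 11, gives the same cycle limits with a different scope: "magrolimab+venetoclax+azacitidine in Cohort 1 and before the third cycle of magrolimab + MEC in Cohort 2".

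Run-in patients are in the analysis. Sections 2.1 and 2.2 list EFS under headings that join the safety run-in and Phase 2 parts. Endpoints meant for one part only carry a label there, and EFS carries none. Section 8.3.1.1 says "The FAS includes all enrolled patients who receive at least 1 dose of any study treatment". Section 8.5.2 says that the EFS quartiles and the event-free proportions at Weeks 12, 24 and 48 "will be estimated by cohort using the KM method".

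**The concern.** Section 3.1 uses *Safety Run-in Cohort* and *Phase 2 Cohort* as names for different groups, so the qualifier in Section 8.1.3 has a literal meaning. On that meaning, a run-in patient who never reaches CR cannot have a treatment-failure event and cannot relapse from CR. Death is the only EFS event left, and otherwise the patient is censored at the last response assessment. Under Appendix 7 the same patient is an event on Day 1.

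Following Section 8.1.3 to the letter puts two event definitions into one Kaplan-Meier curve. Non-responders in the run-in part stay at risk, or are censored for reasons tied to their non-response, while non-responders in Phase 2 drop out on Day 1. Censoring is a realistic outcome. Section 3.3 takes Cohort 2 patients without an objective response after two cycles off therapy, and Appendix Table 9 schedules no response assessment after the end-of-treatment visit. The error runs one way, towards longer EFS.

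**Working it through.** **The plan's own figure.** The protocol gives no numerical assumption for EFS. Its one related figure is the Cohort 2 power in Section 8.10 (36 patients = 30 Phase 2 + 6 run-in, CR 35% against 19%, one-sided alpha 0.1). With the one-sample score approximation:

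Φ[((0.35 − 0.19) − 1.2816 × √(0.19 × 0.81/36)) / √(0.35 × 0.65/36)] = Φ[(0.16 − 0.0838)/0.0795] = Φ(0.959) = 0.831

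This matches the stated 83.1%. It also shows that the protocol itself pools run-in and Phase 2 patients in Cohort 2.

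**Inputs for the EFS check**
- Cohort 1: N = 18, of whom R = 7 run-in (Section 3.1.3).
- Cohort 2: N = 36, of whom R = 6 run-in (Section 8.10).
- CR rate p, Cohort 2: 35% (target) and 19% (historical), both from Section 8.10.
- CR rate p, Cohort 1: this version states no target. 43% is the venetoclax + azacitidine rate in Section 1.3.3, and 37% is the rate in Section 1.1.2.1. The upper value of 65% is an assumption.
- Run-in and Phase 2 patients are assumed to share the same p, and p is taken as the CR rate reached within the cycle limit.

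**Step just after Day 1**
- Appendix 7 reading: every patient without CR is an event, so the curve stands at p.
- Section 8.1.3 reading: only Phase 2 patients without CR are events, so the curve stands at p + (R/N)(1 − p).
- Gap = (R/N)(1 − p), compared with SE = √(p(1 − p)/N).

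| Cohort | p | Appendix 7 | Section 8.1.3 | Gap | SE | Gap/SE |
|---|---|---|---|---|---|---|
| 1 | 0.37 | 0.370 | 0.615 | 0.245 | 0.114 | 2.15 |
| 1 | 0.43 | 0.430 | 0.652 | 0.222 | 0.117 | 1.90 |
| 1 | 0.65 | 0.650 | 0.786 | 0.136 | 0.112 | 1.21 |
| 2 | 0.19 | 0.190 | 0.325 | 0.135 | 0.065 | 2.06 |
| 2 | 0.35 | 0.350 | 0.458 | 0.108 | 0.079 | 1.36 |

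For example, Cohort 1 at 43%: (7/18) × 0.57 = 0.222, and √(0.43 × 0.57/18) = 0.117.

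**Median.** In Cohort 2 both curves are below 0.5 straight after Day 1 at either CR rate, so the median is Day 1 under both readings. In Cohort 1 at 37% or 43%, the Appendix 7 curve is below 0.5 (median Day 1) and the Section 8.1.3 curve is above it (median later). At 65% neither reading puts the median on Day 1.

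**Reporting times.** The gap at Weeks 12, 24 and 48 depends on how long run-in patients without CR survive and when they are censored. It was simulated in 16 scenarios:
- p of 19% and 35% in Cohort 2, and 43% and 65% in Cohort 1.
- Median survival of patients without CR assumed at 3 or 5 months in Cohort 2 (the range in Section 1.4.4) and at 5 or 9.6 months in Cohort 1.
- Median remission assumed at 8 months in Cohort 2 and 18 months in Cohort 1.
- Censoring of run-in patients without CR at Day 56, or not at all.

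| Time | Cohort 1 gap (points) | Cohort 2 gap (points) | Gap/SE, all scenarios |
|---|---|---|---|
| Week 12 | 9.4 to 18.8 | 5.8 to 9.7 | about 0.7 to 1.7 |
| Week 24 | 6.5 to 16.8 | 3.1 to 7.6 | about 0.4 to 1.5 |
| Week 48 | 2.6 to 13.7 | 0.6 to 4.8 | about 0.1 to 1.2 |

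The gap is below 1 SE in 10 of 16 scenarios at Week 24 and in 13 of 16 at Week 48.

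**The case against.** The best defence is that *Phase 2* in Section 8.1.3 is a leftover word. The bullet's own label covers Cohorts 1 and 2. The amendment history records a single EFS update touching both Section 8.1.3 and Appendix 7, which points to one intended definition. The protocol is also loose with the term elsewhere: Section 8.1.2 ties the primary CR rate to the Phase 2 cohorts, while Section 8.10 counts the 6 run-in patients in its sample size. Nothing suggests that the sponsor meant to exempt run-in non-responders. This makes the Appendix 7 reading the likelier intention, but no sentence says which text governs, so the conflict stands.

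The defence is also right that the stakes are limited. EFS is a secondary, single-arm, descriptive summary without a test.

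A reader might infer more than the documents support:
- That run-in non-responders never fail, or count as event-free throughout. They do not: death from any cause is an event for every patient, and the others are censored.
- That the whole curve shifts by 1 to 2 standard errors. That describes only the step just after Day 1, which is not a reporting time.
- That the gap will certainly widen if Cohort 2 de-escalates and adds run-in patients. That holds only if patients from abandoned dose levels are pooled into the curve, and the protocol states pooling only for the 30 + 6 in the CR sample size.

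**Conclusion.** The two current definitions contradict each other for patients who are in the analysis, and the Section 8.1.3 text makes EFS look better. Just after Day 1 the size is about 22 points in Cohort 1 at an assumed 43% CR rate (1.2 to 2.2 SE over 65% to 37%) and 11 to 14 points in Cohort 2 (1.4 to 2.1 SE over 35% to 19%). At the reported weeks the difference is smaller and rests on assumed survival and censoring. A change in the median is shown only for Cohort 1, and there the move off Day 1 depends on the CR rate. With 6 run-in patients and these CR rates, Cohort 2 has a Day 1 median either way. The primary CR analysis and its 83.1% power are untouched. The point is worth settling before analysis, because in an open-label single-arm study an unresolved choice of event definition would otherwise be made with the outcomes in view.

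**What to change.** In Section 8.1.3, delete *Phase 2* from both parts of the treatment-failure definition, so that it refers to Cohort 1 and Cohort 2. It then agrees with Appendix 7, with the endpoint's own label, and with the by-cohort analysis on the Full Analysis Set. The cost is a one-line wording change. It needs no new data, and the reported EFS becomes slightly less favourable.

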6.4. Efficacy Assessments

Clinical response will be assessed by the investigator using prespecified criteria (Appendix 7).

Response assessments will be done in conjunction with bone marrow assessments, according to the schedule of assessments (Appendix Table 2 and Appendix Table 3). Bone marrow assessments (including aspirate and core/trephine biopsy) are required for response assessments and may be used for blast evaluation, MRD assessment, cytogenetics, RO (to be collected at selected study sites), and correlative studies. Peripheral blood smears for blasts should be done on the day of the bone marrow assessments. Details for preparation and distribution of aspirate and biopsy/trephine specimens to the testing laboratories will be provided in the laboratory manual for this study.

If the patient is cytopenic at the time of the bone marrow assessment, CBC is to be monitored at least once per week until optimal count recovery is reached. The best accompanying laboratory CBC result within the \pm 2-week window is to be used to support an efficacy response assessment, with the date of response assigned as the date of bone marrow assessment. If a patient achieves a CR, subsequent bone marrow biopsies are still required to be performed in accordance with the schedule of assessments

Bone marrow aspirate and biopsy slides or blocks for efficacy assessments will be prepared for potential evaluation of response assessments by independent central review.

Response assessment will be obtained at the EOT visit unless a prior response assessment has been performed within the last 30 days or progressive disease has been documented.

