- c The serum pregnancy test collected at screening may be used as the Cycle 1 Day 1 test if performed within 72 hours of first dose of study treatment. Urine or serum pregnancy tests will be conducted every 4 weeks following Cycle 1 Day 1 and can be performed locally without a requirement to visit the study site; additional guidance is provided in Section 6.5.1.
- d Pretreatment assessments for the initial dose (Cycle 1 Day 1) may be collected up to 72 hours before administration of any study treatment except for Hb, which must be performed within 24 hours prior to magnolimab dosing. Thereafter, pretreatment assessments are to be collected within 24 hours prior to any intravenous/subcutaneous study drugs during the first 2 weeks and within 72 hours prior to any intravenous or subcutaneous study drugs thereafter.
- e Additional samples for CBC may be collected outside of the protocol-specified time points to ensure a WBC level $\leq 20 \times 103/\mu$ L prior to each magnolimab dose during Cycle 1.
- f Vital signs will be assessed prior to administration of any study treatment. Details are provided in Section 6.5.4.
- g Adverse events and concomitant medications should be recorded at all scheduled and unscheduled assessment visits, and at all treatment visits, even when other assessments are not scheduled.
- h Samples will be collected predose within 12 hours prior to study treatment administration. Peripheral blood for correlative studies does not need to be repeated at Cycle 2 Day 1 if done at Cycle 1 Day 28 within 3 days of Cycle 2 Day 1.
- i At each bone marrow time point, both trephine (biopsy) and aspirate samples are to be collected for correlative studies.
- j Samples for RO will be collected at selected study sites.
- k Samples will be collected on Day 28 of Cycles 4, 6, 9, 12, and 15.
- 1 A trephine (biopsy) is to be collected for response assessment. An aspirate sample will be collected for response assessment and MRD assessment. Response assessments may be adjusted by ± 1 week for Day 28 of Cycles 1 and 2. After Cycle 2 Day 28, the window is ± 14 days. Conventional cytogenetics to be tested per institutional standards. m Samples will be collected on Day 28 of Cycles 4 and 6, and then every 3 cycles thereafter during study treatment.
- n Single sample will be collected on Day 1 or at any time during the study.
- o Peripheral blood smears for blasts are to be collected along with bone marrow aspirate/biopsy and assessed locally.

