- a If patient achieved blast clearance after Cycle 1, one additional cycle of MEC will be given (total 2 cycles). If patient achieved blast clearance only after Cycle 2, a third cycle of MEC will be given. If no blast clearance at the end of Cycle 2, patient should be discontinued from the study.
- b Any other visit window specifications for individual assessments should be applied.
- c The serum pregnancy test collected at screening may be used as the Cycle 1 Day 1 test if performed within 72 hours of first dose of study treatment. Urine or serum pregnancy tests will be conducted every 4 weeks following Cycle 1 Day 1 and can be performed locally without a requirement to visit the study site; additional guidance is provided in Section 6.5.1.
- d Pretreatment assessments for the initial dose (Cycle 1 Day 1) may be collected up to 72 hours before administration of any study treatment except for Hb, which must be performed within 24 hours prior to magrolimab dosing. Thereafter, pretreatment assessments are to be collected within 24 hours prior to any intravenous/subcutaneous study drugs during the first 2 weeks and within 72 hours prior to any intravenous or subcutaneous study drugs thereafter.
- e Vital signs will be assessed prior to administration of any study treatment. Details are provided in Section 6.5.4.
- f Adverse events and concomitant medications should be recorded at all scheduled and unscheduled assessment visits, and at all treatment visits, even when other assessments are not scheduled.
- g Samples will be collected predose within 12 hours prior to study treatment administration.
- h Samples for receptor occupancy will be collected at selected study sites.
- i At each bone marrow time point, both trephine (biopsy) and aspirate samples are to be collected for correlative studies.
- j A trephine (biopsy) is to be collected for response assessment. An aspirate sample will be collected for response assessment and MRD assessment. Response assessments may be adjusted by ± 1 week for Day 28 of Cycles 1 and 2. After Cycle 2 Day 28, the window is ± 14 days. Conventional cytogenetics to be tested per institutional standards.

- k Single sample will be collected on Day 1 or at any time during the study.

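### EFS treatment failure is cut off at the start of a cycle: in Cohort 1 a first CR on an in-window Cycle 4 marrow can become a Day 1 event, and in Cohort 2 patients without a third MEC cycle have no cut-off

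*Protocol*

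**What the plan says.** **The rule.** For Cohort 1, Section 8.1.3 defines EFS treatment failure as "failure to achieve CR before the fifth cycle of magrolimab+venetoclax+azacitidine in Phase 2 Cohort 1". For Cohort 2 the cut-off is "before the third cycle of magrolimab + MEC in Phase 2 Cohort 2". Appendix 7 repeats both cut-offs. Section 8.1.3 adds: "Day 1 of treatment will be assigned as the event date for patients with treatment failure".

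**Dating of a response.** Under Section 6.4 a response is supported by the best blood count within two weeks either side of the marrow, "with the date of response assigned as the date of bone marrow assessment".

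**Cohort 1 schedule.** Appendix Table 2 places response marrows at Day 28 of Cycles 1 and 2. After that, footnote m states: "Samples will be collected on Day 28 of Cycles 4 and 6, and then every 3 cycles thereafter during study treatment". Footnote l sets the timing: "After Cycle 2 Day 28, the window is ± 14 days".

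**Cohort 2 pathways.** Section 5.3 starts a cycle on the first day of MEC. Appendix Table 3, footnote a, reads: "If patient achieved blast clearance after Cycle 1, one additional cycle of MEC will be given (total 2 cycles". The same footnote gives a third MEC cycle only to patients whose blasts clear after Cycle 2, and discontinues patients with no clearance at the end of Cycle 2. Table 2, Table 5 and Appendix Table 7 carry the same footnote.

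**Primary endpoint.** Section 8.1.2 counts any CR on study before new anti-AML therapy, with no limit by cycle.

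**The concern.** The cut-off is a treatment date, but the evidence for CR is a marrow with its own visit window. If the window runs past the treatment date, a site can follow the schedule exactly, document a first CR, and still have the patient scored as a failure. Because failures are dated to Day 1, the error is not a small shift in time: a responder becomes an event at time zero. The reported quartiles and the Week 12, 24 and 48 proportions (Section 8.5.2) can all be affected.

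In Cohort 2 the cut-off refers to a cycle that some patients never receive by design. EFS then depends on how many MEC cycles a patient was given as well as on the disease course, and two analysts could derive different results from the same data.

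**Working it through.** **1. The plan's own sizing figure.** The only one is the 83.1% power for the Cohort 2 CR test (Section 8.10): n = 36, null 0.19, alternative 0.35, 1-sided alpha 0.1. The normal approximation is Φ{[(0.35 − 0.19)√36 − 1.2816·√(0.19 × 0.81)] / √(0.35 × 0.65)} = Φ{(0.960 − 0.503)/0.477} = Φ(0.959) = 0.831. It reproduces. It concerns CR, not EFS, and nothing below changes it.

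**2. Cohort 1 day count (28-day cycles, no delay).**
- Cycle 4 Day 28 = 4 × 28 = Day 112.
- Permitted marrow window = 112 ± 14 = Days 98 to 126, which is 29 days.
- Cycle 5 Day 1 = Day 113.
- Permitted days on or after the cut-off: Days 113 to 126 = 14 of 29.
- If Cycle 5 Day 1 moves within its ± 3-day visit window, the count runs from 17 (Day 110) to 11 (Day 116).
- If Cycle 5 starts d days late, the overlap is 126 − (113 + d) + 1 = 14 − d days. It disappears at a 14-day delay.

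No response marrow is scheduled in Cycle 3, so Cycle 4 Day 28 is the only one between the Cycle 2 marrow and the cut-off. A first CR on a Day 110 marrow is on time. The same CR on a Day 115 marrow, equally within the window, is a Day 1 failure.

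**3. Size per patient, Cohort 1.** With 18 patients enrolled (7 run-in, 11 Phase 2) and all in the Full Analysis Set, one reclassified patient costs 1/18 = 5.6 points from time zero. The loss lasts until that patient would otherwise have had an event or been censored. It does not persist over the whole curve.

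**4. Cohort 2 pathways.**

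| Blast clearance | MEC cycles | Date of the cut-off |
|---|---|---|
| After Cycle 1 | 2 | none: no third cycle |
| Only after Cycle 2 | 3 | first day of third MEC cycle |
| Not by end of Cycle 2 | 2, then discontinued | none: no third cycle |

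Take two patients who both have CRi, not CR, at the Cycle 2 marrow (nominal Week 8). Appendix Table 3 puts the next response marrow 8 weeks after the end of MEC.
- Two-cycle patient: 8 + 8 = Week 16. A first CR there is still before a third cycle that never comes, so read literally the patient is not a failure.
- Three-cycle patient: 12 + 8 = Week 20. A first CR there comes after the third cycle started, so the patient is a Day 1 failure.

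The literal reading therefore favours two-cycle patients with a late CR. The gap matters mainly for this group, because patients who never clear blasts leave treatment without a CR.

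**The case against.** **A stronger reading that the documents do not support.** A reader might infer that the same window overlap affects Cohort 2. The Cycle 2 marrow is allowed on Days 49 to 63 ("Response assessments may be adjusted by ± 1 week for Day 28 of Cycles 1 and 2"), and nominal Cycle 3 Day 1 is Day 57. But the rule names no study day, and a third MEC cycle is given only once clearance after Cycle 2 is known, so that marrow should come before Cycle 3. A late marrow moves Cycle 3 later. Where there is no Cycle 3, Day 57 is not a cut-off at all. Nor does a missing third cycle turn remissions into Day 1 events: read literally, it makes late CRs non-failures. The protocol also gives no figure for how many Cohort 2 patients stop at two cycles, so no claim about a majority can be made.

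**Points that limit Cohort 1.** The overlap needs a patient with no CR at the Cycle 1 or Cycle 2 marrow, a Cycle 4 marrow taken in the late part of its window, and Cycle 5 already started. Late count recovery alone is covered, since the response keeps the marrow date. Table 9 delays the next cycle for prolonged Grade 4 cytopenia after remission, which moves the cut-off later. The 14 of 29 counts permitted days and is not a misclassification rate. All of this stands.

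**Landmark and SAP.** Any landmark rule will score some later CRs as EFS failures, and Amendment 6 changed the EFS definition deliberately to align it with other magrolimab AML studies. That is fair for CRs after the deciding assessment. It does not cover a CR shown at that assessment within its allowed window. Mapping visits to landmarks is often left to the SAP, but here the protocol fixes the cut-off itself, in two places.

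**Conclusion.** The point holds, and it concerns a secondary endpoint. In Cohort 1 the stated rule can score a protocol-compliant first CR as a Day 1 event, on up to 14 of 29 permitted marrow days if Cycle 5 starts on schedule and on fewer if it is delayed. Each such patient is worth about 5.6 points on the Kaplan-Meier curve for a limited time. How many patients are affected cannot be known from the protocol.

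In Cohort 2 the defect is an undefined cut-off for patients without a third MEC cycle. Taken literally, it treats the same late CR differently by number of MEC cycles, in the two-cycle patients' favour.

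The day counts assume 28-day cycles, and the per-patient size assumes all 18 Cohort 1 patients are analysed together. The primary CR analysis and its 83.1% power are unaffected.

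**What to change.** In both Section 8.1.3 and Appendix 7, define treatment failure as failure to achieve CR at or before the Cycle 4 Day 28 (Cohort 1) or Cycle 2 Day 28 (Cohort 2) response assessment. Count an assessment done within its allowed window, regardless of whether or when a further cycle is given.

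With this wording the Cohort 1 in-window days that fall after the cut-off go from 14 to 0. Every Cohort 2 pathway has the same cut-off.

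The cost is a wording change in two places, with no new data and no change to treatment. Any late-window first CRs in Cohort 1 stop being Day 1 events. The downside is that some two-cycle Cohort 2 patients with a late CR become failures, which is the price of treating them like three-cycle patients.
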